1. OBJECTIVES

1.1. Primary Objective

The differentiation between malignant bone sarcomas, especially Ewing sarcomas, and a subacute osteomyelitis can be difficult based on imaging tests (1-4). Biopsy, curettage and/or cultures of the lesion may be necessary to establish a diagnosis. These procedures are invasive and time-consuming, causing delay in treatment and significant anxiety of the patients and their parents. **The goal of our project is to establish a novel, non-invasive, immediately clinically applicable imaging test for the differentiation of bone sarcomas and osteomyelitis.** Our approach relies on the FDA-approved iron supplement drug ferumoxytol (Feraheme), which is used in patients for intravenous treatment of iron deficiency (5-8). Ferumoxytol is composed of iron oxide nanoparticles, which provide a strong T1- and T2-signal on magnetic resonance (MR) images and, thus, can be used as an MR contrast agent (9, 10). *We hypothesize, that MR images after intravenous injection of ferumoxytol will demonstrate a significantly stronger T1- and T2-enhancement of osteomyelitis when compared to malignant bone sarcomas.* The T1-effect of ferumoxytol is dependent on its ability to interact with protons in the target tissue (9, 14, and 21). Thus, we expect to find a significantly stronger T1-enhancement of edematous inflammations as opposed to highly cellular tumors. In addition, ferumoxytol is phagocytosed by local macrophages, which leads to a persistent MR signal defect on 24 h delayed T2-weighted MR images (9). Thus, we expect to find a significantly stronger T2-enhancement of macrophage-rich inflammations as opposed to bone sarcomas with relatively few tumor-associated macrophages in their stroma.

We will investigate the following specific aims:

- 1) Establish MR imaging characteristics of bone sarcomas and osteomyelitis based on their ferumoxytol-enhancement on relatively early postcontrast T1-weighted images.
- 2) Establish MR imaging characteristics of bone sarcomas and osteomyelitis based on their ferumoxytol-enhancement on delayed postcontrast T2-weighted images.

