2.4 Study Design

Diagnostic: The goal of our project is to establish a novel, non-invasive, immediately clinically applicable imaging test for the differentiation of bone sarcomas (osteosarcomas and Ewing sarcomas) and osteomyelitis. Our approach relies on the FDA-approved iron supplement drug ferumoxytol (Feraheme), which is used in patients for intravenous treatment of iron deficiency. Ferumoxytol is composed of iron oxide nanoparticles, which provide a strong T1- and T2-signal on magnetic resonance (MR) images and, thus, can be used as an MR contrast agent. Based on our extensive experience with pre-clinical and clinical imaging applications of iron oxide nanoparticles, we hypothesize that MR image after intravenous injection of ferumoxytol will demonstrate a significantly stronger T1- and T2- enhancement of osteomyelitis when compared to malignant bone sarcomas.

Hypotheses:

(1) *Bone sarcomas and osteomyelitis show a different T1-enhancement at 1 h post injection (p.i.) of ferumoxytol*

(2) *Bone sarcomas and osteomyelitis demonstrate differences in T2-enhancement at 24 h p.i. of ferumoxytol*

We plan to enroll 20 patients in this study, 10 patients with bone sarcomas and 10 patients with an osteomyelitis. The sample size has been determined based on our preliminary data and power calculations. We will screen all patients with proven or suspected bone sarcoma or osteomyelitis for potential participation in this study. Inclusion criteria will comprise an age of 10-21 years (we do not include younger patients in order to exclude need of sedation) and a suspected or confirmed diagnosis of a bone sarcoma or osteomyelitis. Exclusion criteria comprise MR-incompatible metal implants, need of sedation (since an anesthesia is not supported by this), claustrophobia or hemosiderosis/hemochromatosis. All patients will undergo two subsequent imaging tests on a 3T MR scanner, using dedicated surface coils for high resolution MR imaging. During the first MR examination, ferumoxytol will be injected intravenously at a dose of 5 mg Fe/kg:

(A) MRI before and up to 1 h after injection of ferumoxytol for evaluation of lesion perfusion, blood volume, microvascular permeability and interstitial retention (enhanced permeability and retention effect of macromolecules)

(B) 24h after (A): Follow up MRI for evaluation of macrophage phagocytosis

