Of note, the PI of this proposed study has applied USPIO as MR contrast agents in phase II and III clinical trials in adult patients (11, 13, 14, and 20). These contrast agents are very well tolerated and show excellent safety profiles (5-8). The delivered iron dose via a typical ferumoxytol administration is in the order of 150-500 mg iron oxides (note that these are coated iron particles, not free iron), which is equivalent to or lower than the iron dose administered with one blood sample. USPIO are slowly metabolized in the liver and not excreted via the kidneys. Thus, they are safe to use in patients with renal insufficiencies and are not associated with any risk of nephrogenic sclerosis (a potential adverse event after injections of certain gadolinium chelates). Anaphylaxis or anaphylactoid reactions were reported in 0.2% of a subject, which is in the order of or lower compared to other MR contrast agents (see FDA report, ref. 6).

Figure 1: MR signal characteristics of bone marrow tumors with USPIO, as demonstrated in a patient with Non-Hodgkin's lymphoma after chemotherapy and GCSF therapy. (A) T1-weighted MR images before contrast media administration show a hypercellular reconverted bone marrow, which demonstrates diffusely decreased signal due to its high cellularity. Two focal lesions are noted (arrows). (B) T1-weighted MR images after intravenous administration of the USPIO ferumoxtran-10 (Sinerem / Combidex) do not show any T1-enhancement (positive contrast) of these lesions. (C) Precontrast STIR images show a relatively high signal of the hypercellular reconverted bone marrow with focal, more hyperintense lesions (arrows). (D) STIR images after intravenous administration of ferumoxtran-10 show a marked, diffuse T2-enhancement (negative contrast, signal loss) of the normal bone marrow due to phagocytosis of the agent by macrophages in normal bone marrow. Focal neoplastic lesions (arrows) contain no or few macrophages and stand out as bright lesions (arrows).

[figure not shown]
[figure not shown]

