6. DOSE MODIFICATIONS

Dose modification scheme:

- (A) Serious anaphylactoid reactions are not dose dependent. Thus, in case we should observe an increased incidence of severe anaphylactoid reactions, i.e. more than one patient in our limited study population of 20 patients, or if any of our patients encounters a permanent impairment due to the ferumoxytol administration, the study will be terminated.
- (B) In case we should observe an unexpected decrease in blood pressure of more than 10% in more than one patient via blood pressure measurements or in case we observe severe nausea in more than one patient, we will successively decrease the administered dose by 1 mg/kg until event-free tolerance is achieved. Of note, our colleagues from Oregon Health & Science University (see below) reported no such side effects of ferumoxytol in their population of children with brain tumors.
- (C) Precontrast MR scans will serve as an internal standard. We will measure the signal intensity of sarcomas and osteomyelitis and divide this signal by the signal of normal muscle to normalize for potential MR spectrometer variations over time. We expect at least 20% tumor/muscle enhancement on post-contrast T2-weighted MR scans compared to precontrast scans. If this enhancement will not be achieved, but ferumoxytol is well tolerated, we will increase the administered dose to 6 mg Fe/kg with a maximum total amount of 510 mg Fe (FDA-approved dose for single injection).

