- (D) In the unlikely event, that the T1- and T2-enhancement of both pathologies exceeds 500%, we have reached a plateau of contrast agent accumulation for both pathologies rather than depicting an expected relative limited accumulation of ferumoxytol in sarcomas compared to osteomyelitis. Based on our experience with pre-clinical and clinical iron oxide applications, we expect that maximal difference between sarcomas and osteomyelitis occur with the highest dose. This is the reason why we limit our study population to this dose for this initial pilot study. In the unlikely event that contrast agent accumulation reaches a plateau in both of these pathologies or no enhancement is noted on MR scans, we will terminate the study after evaluation of n=6 patients (MR data from n=6 patients should allow evaluation of significant differences between quantitative pre- and post-contrast signal intensities via a t-test). We have submitted an R21 NIH grant proposal which would allow more extensive evaluation of patient subgroups (n=5), examined with decreasing ferumoxytol doses.

Stopping rules for an individual test:

- (A) To avoid paravasal injections, the peripheral venous access will be checked with a saline flush prior to contrast media injection. In case of any swelling or discoloration at the ferumoxytol injection site (in the extremely rare event of a paravasal injection despite prior uncomplicated saline injection), the ferumoxytol injection will be stopped immediately, a new peripheral venous access will be placed at the contralateral extremity and the remaining ferumoxytol will be slowly administered. In case a local reaction is observed again, the ferumoxytol injection will be discontinued completely.

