- (B) If we observe a decline in blood pressure during the contrast media injection, we will discontinue the ferumoxytol injection immediately (in the experience of the PI, a transient hypotension represents a possible AE). In case we observe any signs of a potential anaphylactoid reaction (e.g. significant hypotension > 10% with associated tachycardia or bradycardia) during the contrast media injection, the injection will be discontinued immediately. Patients with mild symptoms such as urticaria, pruritus, rhinorrhea, nausea, diaphoresis and/or coughing will be observed for resolution of symptoms or progression. Patients, who show severe and/or progressive symptoms, such as arrhythmias, severe hypotension, breathing difficulties, dizziness or vomiting will be treated immediately by the M.D. on site and the Pediatric Emergency Care team will be

notified for immediate assistance.

Stopping rules for the study:

- (A) In case of any serious AE, that leads to persistent impairment of a study patient, the study will be terminated.
- (B) Anaphylactoid reactions are a possible, but rare side effect of any contrast agent, reported in 1% of patients receiving Gd-based contrast agents and 1% of patients receiving ferumoxytol. In case we observe an increased incidence of severe anaphylactoid reactions, i.e. more than one patient in our limited study population of 20 patients, the study will be terminated.
- (C) According to our statistician, the study population of n=10 patients with sarcomas and n=10 patients with osteomyelitis is already very limited and considered a pilot population to demonstrate major differences in ferumoxytol enhancement of these two pathologies. In the unlikely event, that contrast enhancement reaches a plateau in both pathologies or no enhancement at all is noted in these pathologies on MR scans, neither on T2-weighted MR scans nor on T1-weighted MR scans, the study will be terminated after evaluation of n=6 patients (MR data from n=6 patients should allow evaluation of significant differences between quantitative pre- and post-contrast signal intensities via a t-test).

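### The dose-increase rule in 6(C) does not say which lesions count; read on sarcomas it can fire on the weak uptake the plan hypothesises, and 11.2 has no provision for mixed doses

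*Combined protocol and SAP*

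**What the plan says.** All patients are to receive 5 mg Fe/kg once. Section 6(C) normalises lesion signal, for sarcomas and osteomyelitis, to muscle. It then sets the expectation "We expect at least 20% tumor/muscle enhancement on post-contrast T2-weighted MR scans compared to precontrast scans" and continues: "If this enhancement will not be achieved, but ferumoxytol is well tolerated, we will increase the administered dose to 6 mg Fe/kg", capped at 510 mg Fe. Section 6(B) allows movement the other way for hypotension or nausea: "we will successively decrease the administered dose by 1 mg/kg until event-free tolerance is achieved".

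The scientific premise is that sarcomas take up less agent. Section 1.1 expects stronger T2 enhancement in inflammation "as opposed to bone sarcomas with relatively few tumor-associated macrophages in their stroma". Section 2.4 makes this Hypothesis 2: "Bone sarcomas and osteomyelitis demonstrate differences in T2-enhancement at 24 h p.i. of ferumoxytol". Section 6(D) refers to the dose "rather than depicting an expected relative limited accumulation of ferumoxytol in sarcomas compared to osteomyelitis", and says that the pilot is limited to one dose.

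Time point and sign are settled outside 6(C). Section 9.1 places T2 at 24 hours, and Figure 1 in section 2.5 describes "T2-enhancement (negative contrast, signal loss) of the normal bone marrow".

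Section 9.1.3 measures bone marrow as a positive internal standard for contrast accumulation; 6(C) does not refer to it. Section 11.2.1 takes in all images of the study population. Section 11.2.2 gives descriptive statistics per group, the area under the ROC curve and a Wilcoxon rank sum test, with no dose stratum, covariate or subset.

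**The concern.** A weak T2 effect in sarcomas has two explanations: the tumours hold few macrophages, which is the hypothesis, or the dose is too low to give a measurable signal. If 6(C) is applied to sarcomas, both lead to the same dose increase. The early stop after six patients does not fill the gap, because it applies when "contrast enhancement reaches a plateau in both pathologies or no enhancement at all is noted in these pathologies on MR scans". Weak sarcoma with strong osteomyelitis falls outside it.

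The trigger is a muscle-normalised form of the primary T2 outcome, so early outcomes can set the dose of later patients. Two investigators could also read the same data differently, since neither the lesions nor the unit of decision is fixed. If the dose does change, a patient dosed under 6(C) still follows the protocol and stays in the analysis. The 10 v 10 comparison then mixes doses. At stake is which dose the estimates describe and, if dose and diagnosis become linked, part of the comparison itself.

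**Working it through.** **Plan's own figures.** A two-sample t-test with 10 per group, 18 degrees of freedom, a difference of 1.33 SD and two-sided 5% (assumed; the plan gives no level) has power 80.3%, against 80% in 11.3.2. P(χ²₁₈ < 0.8 × 18) = 29.7% and P(χ²₁₈ < 0.5 × 18) = 4.0%, against the stated 30% and 4%. All reproduce. They presuppose one distribution per group, hence one dose.

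**Assumptions for the rest.** The documents give no means, SDs or accrual ratio. Taken here, in percentage points of T2 signal loss at 5 mg/kg: sarcoma mean m = 10, 20 or 30 with SD 10; osteomyelitis mean 40 with SD 15; mean proportional to dose; SD within a dose unchanged.

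**1. Chance that the rule fires (threshold 20).** One sarcoma: Φ((20 − m)/10). Mean of three sarcomas: Φ((20 − m)/(10/√3)). Mean of three of each lesion: Φ((20 − (m + 40)/2)/5.20), where 5.20 = √((100/3 + 225/3)/4).

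| Reading | m = 10 | m = 20 | m = 30 |
|---|---|---|---|
| One sarcoma | 84% | 50% | 16% |
| Mean of 3 sarcomas | 96% | 50% | 4% |
| Mean of 3 + 3 lesions | 17% | 3% | 0.2% |

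Which lesions count largely decides whether the dose changes.

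**2. Balanced escalation (half of each group at 6 mg/kg, m = 10).** The mean difference goes from 30 to 30 × 1.1 = 33. The dose step adds a variance of (0.1 × mean)²: sarcoma 100 to 101, osteomyelitis 225 to 241. Pooled SD goes from √162.5 = 12.75 to √171 = 13.08. The standardised difference goes from 30/12.75 = 2.35 to 33/13.08 = 2.52. A future sample size based on it changes by (2.35/2.52)² ≈ 0.87, a fall of about 13%.

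**3. Unbalanced escalation.** Suppose the step follows the third sarcoma and osteomyelitis accrues r times as fast. Then 3 sarcomas and 3r osteomyelitis patients receive 5 mg/kg and the rest 6. The sarcoma mean dose is 5.7. For m = 10 the difference is 8 × (osteomyelitis dose) − 2 × 5.7; for m = 20 it is 8 × (osteomyelitis dose) − 4 × 5.7. The comparator is the plan, 5 mg/kg for all: 30 and 20.

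| Osteomyelitis : sarcoma | Osteomyelitis mean dose | Difference, m = 10 | Difference, m = 20 |
|---|---|---|---|
| 1:1 | 5.7 | 34.2 (+14%) | 22.8 (+14%) |
| 2:1 | 5.4 | 31.8 (+6%) | 20.4 (+2%) |
| 3:1 | 5.1 | 29.4 (−2%) | 18.0 (−10%) |

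**4. No true difference.** Wilcoxon test with critical values U ≤ 23 or ≥ 77, 40,000 simulated trials, same mean in both diseases, enhancement ×1.2 at 6 mg/kg. With one dose, rejection is about 4%. With 7 sarcomas and 4 osteomyelitis patients at 6 mg/kg (the 2:1 case) it is 4% to 5%. With 7 and 1 (the 3:1 case) it is 6% at mean 20, SD 10; 8% at mean 25, SD 10; and 13% at mean 20, SD 5. The extra rejections favour stronger enhancement in sarcoma, the opposite of the hypothesis. The simulation ignores that the step itself follows low early sarcoma values.

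**The case against.** The strongest reply is that 6(D) gives a reason for dosing high: the investigators expect the greatest contrast between the diseases at the highest dose. On that view a rise to 6 mg/kg, within the approved single dose, helps whether sarcoma uptake is weak or the dose is low, so the rule need not tell them apart. Steps 2 and 3 partly bear this out. It does not answer which lesions count, or how two doses are analysed when 6(D) intends one.

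Second, the sentence before the 20% figure covers both pathologies, so tumor may be loose wording for any lesion. That reading is fair, and on it the rule rarely fires under these assumptions. The text does not settle it.

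Third, a reader might infer that the plan predicts sarcomas below 20%, so that success would trigger escalation by design. The documents do not support this. The limited uptake in 1.1 and 6(D) is relative to osteomyelitis, and 6(C) itself expects at least 20%; sarcoma at 25% and osteomyelitis at 60% would fit the hypothesis without triggering.

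Fourth, pooling across doses is inferred from silence in 11.2. The case report form records dose and injected volume, so reporting by dose remains possible. It is not planned.

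**Conclusion.** The point stands as a gap in a stated rule, with small expected harm. 6(C) leaves open the lesions and the unit of decision. On a sarcoma reading it cannot separate a supportive result from an inadequate dose; on an all-lesion reading it fires much less often. Any change under 6(B) or 6(C) would be analysed with no dose term.

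A reader might also infer that escalation shrinks the difference between diseases, or enlarges a future trial by about 5% (171/162.5 = 1.05). Neither follows. Against the planned 5 mg/kg the difference moves by +14%, +6% and −2% at 1:1, 2:1 and 3:1 accrual with a sarcoma mean of 10, and a loss as large as 10% needs both 3:1 accrual and a sarcoma mean of 20. The 5% holds only if the target difference is fixed while the observed one grows. Distortion arises only when dose and diagnosis become unbalanced. Section 11.3.1 (sarcoma rarer) and section 4.2 (each group filled to 10) make that possible, but no accrual ratio is given. All sizes rest on assumed means, SDs and dose-proportionality. Rating: cheap improvement.

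**What to change.** In 6(C), state that low T2 enhancement in sarcomas alone is an outcome and does not trigger an increase. Judge dose adequacy on 24-hour signal loss in confirmed osteomyelitis lesions, since patients may enrol with only a suspected diagnosis. Use the marrow standard from 9.1.3 as supporting evidence, and apply the check at a stated group-level decision point.

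In 11.2.2, if any dose change occurs under 6(B) or 6(C): report results by dose, use an SD pooled within dose and diagnosis, and add a dose-stratified rank-sum test as a sensitivity analysis. The pooled SD stays usable when a cell is small. In the 3:1 case the cells hold 9, 1, 3 and 7 patients and give 8 + 0 + 2 + 6 = 16 degrees of freedom, against 18.

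The cost is a few sentences in section 6, one or two in 11.2.2, and a sponsor decision on threshold and decision point. Marrow signal, dose and injected volume are already collected. The downsides are that marrow does not confirm a measurable lesion signal, and that within-dose results will be imprecise if few patients are at one dose. Whether any dose change should follow a failed check remains a clinical decision for the sponsor.

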2.5 Correlative Studies Background

Our group has worked on MR imaging techniques with iron oxide nanoparticles since 1995 (11-24). We and others have found that intravenously injected USPIO with diameters in the order of 20-50 nm cause a long lasting, positive “blood pool” or vascular enhancement on T1-weighted MR images (9,14,19). In pathologies with an increased microvascular permeability, USPIO extravasate into the interstitium and cause a T1-effect of

the target tissue, which is strongly dependent on the proton content of the interstitial space (among other technical factors). We have thoroughly investigated various factors that lead to an optimized tissue T1-enhancement of USPIO (9, 14, and 19). We have shown that malignant lesions in the bone marrow of patients show nearly no USPIO T1-enhancement, presumably due to their high cellularity, small intercellular space and low proton content (Fig. 1). Inflammations, on the other hand, show a strong T1-enhancement, presumably due to the edematous, proton rich environment (Fig. 2). These data suggest that tumors and inflammations may demonstrate differences in T1-enhancement.

USPIO in the interstitium are subsequently slowly phagocytosed by macrophages in various target tissues, such as liver, spleen, bone marrow or macrophage containing pathologies, where they primarily cause a negative (dark) signal effect on T2-weighted MR images (11,13,18,19,24). Focal malignant tumor lesions in organs of the RES (reticulo-endothelial system) contain no or very few macrophages, thus do not phagocytose USPIO, and stand out as bright lesions (Fig. 1). However, macrophage rich inflammations cause a marked signal loss on delayed T2-weighted MR images (Fig. 2). Thus, we have evidence from a variety of pre-clinical and clinical investigations, that tumors and inflammations may show distinct T2-enhancement patterns.

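### Section 6 does not order dose change and termination when enhancement is absent, its 500% plateau cannot be met as a T2 signal loss, and Section 11.2 ignores dose

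*Combined protocol and SAP*

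**What the plan says.** Four parts of Section 6 bear on this, all in the combined protocol and SAP.

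- Dose modification (B): after certain blood-pressure falls or severe nausea in more than one patient, "we will successively decrease the administered dose by 1 mg/kg until event-free tolerance is achieved".
- Dose modification (C): "We expect at least 20% tumor/muscle enhancement on post-contrast T2-weighted MR scans compared to precontrast scans". The next sentence reads "If this enhancement will not be achieved, but ferumoxytol is well tolerated, we will increase the administered dose to 6 mg Fe/kg", with a cap on total iron. The rule gives no number of patients and no time at which the 20% is judged.
- Dose modification (D): a plateau is reached when "the T1- and T2-enhancement of both pathologies exceeds 500" percent. If there is a plateau in both diseases, or "no enhancement is noted on MR scans, we will terminate the study after evaluation of n=6 patients".
- Study stopping rule (C): the study ends after six patients if there is a plateau, or if "no enhancement at all is noted in these pathologies on MR scans, neither on T2-weighted MR scans nor on T1-weighted MR scans".

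Section 2.5 gives the direction of the T2 effect: "macrophage rich inflammations cause a marked signal loss on delayed T2-weighted MR images". The Figure 1 legend likewise equates T2-enhancement with negative contrast.

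Section 11.2.1 analyses all images and excludes subjects only for missing data or non-adherence. Section 11.2.2 plans descriptive statistics, the area under the ROC curve and the Wilcoxon rank sum test. Neither mentions dose.

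**The concern.** If six patients show no enhancement, one rule tells the team to change the dose and carry on, and another tells them to close the study. A reader of the final report could not tell whether the action taken followed the plan.

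The plateau rule is a second route to closure. Its only number appears to sit on a scale that cannot reach it for T2.

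The analysis then has no provision for the dose changes that Section 6 allows. The study compares enhancement between two diagnoses, and dose plausibly affects enhancement. If a change falls mainly on one diagnosis, the comparison is partly one of doses.

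**Working it through.** **1. The triggers side by side.**

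- Dose modification (C): T2 enhancement below 20%, agent tolerated, any number of patients. Action: change the dose.
- Dose modification (D): no enhancement, sequence not named, six patients evaluated. Action: terminate.
- Study stopping rule (C): no enhancement on T2 and none on T1, six patients evaluated. Action: terminate.

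Zero is below 20%. With six patients evaluated, the agent tolerated and no enhancement seen, (C) and (D) both apply. Study stopping rule (C) applies too if T1 enhancement is also absent. Before six patients only (C) can act. Enhancement above zero but below 20% meets (C) alone.

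**2. The 500% criterion.** Section 6 measures signal intensity (SI) relative to muscle. Percent loss = 100 × (SIpre − SIpost)/SIpre = 100 × (1 − SIpost/SIpre). Signal is not negative, so the loss is at most 100%, also after division by muscle signal. A change above +500% needs SIpost above 6 × SIpre, which is a gain. Rule (D) requires T1 and T2 together, so on this scale it cannot be met.

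Two other scales have no such bound:

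- Section 9.1.3 prints enhancement as (SIpost/SIpre)/SIpre × 100%. Above 500% this needs SIpost/SIpre > 5 × SIpre. With signal loss the ratio is below 1, so SIpre must be below 0.2. The slash may stand for a minus sign, or be an error of text extraction.
- The R2 and R2* relaxation rates of Section 9.1.2 could rise more than sixfold.

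Section 6 names neither.

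**3. Who is analysed.** A patient given a dose changed under (B) or (C) is following the protocol, so the non-adherence exclusion does not apply. Section 4.2 removes and replaces patients with an adverse reaction to the agent, so some who trigger (B) may leave. Later patients who tolerate the changed dose stay, and are analysed with earlier patients given 5 mg Fe/kg.

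**4. Possible size (illustration only).** The plan's own power figure comes first. Ten per group at 1.33 SD, two-sided 5% (assumed; Section 11 states no alpha), t-test with 18 degrees of freedom gives 80.3%, so the stated 80% reproduces. The exact rank sum test on normal data (reject if U ≤ 23 or U ≥ 77, actual size 4.3%) gives about 76%.

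Assumptions: normal data; enhancement proportional to dose, so 6 against 5 mg Fe/kg multiplies it by 1.2; coefficient of variation (CV) 15%, 30% or 50%. None of these comes from the documents.

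Uneven change, 6 of 10 sarcomas and no osteomyelitis patients at 6 mg Fe/kg, no true difference:

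- The sarcoma mean rises by 0.6 × 0.2 = 0.12 of its value. In SD units that is 0.12/CV = 0.80, 0.40 and 0.24.
- Simulated type I error of the exact rank sum test is about 24%, 9–10% and 6%, nearly all of it against the study hypothesis.
- Power at 1.33 SD falls from 76% to 13%, 40% and 53% with the CV set on the sarcoma mean, or 22%, 53% and 65% with it set on the osteomyelitis mean.

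Balanced change after six patients split 3:3, leaving 7 + 7 at the new dose:

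- Type I error is about 2%, 4% and 4%.
- Power is 62%, 72% and 74%, or 67%, 74% and 75%, on the same two bases.

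Large contrast (sarcoma enhancement a quarter of osteomyelitis, assumed) with the uneven change: power stays at 100% at CV 15%, stays above 99% at CV 30%, and falls from 85% to 77–78% at CV 50%.

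**The case against.** The strongest reply is that the rules form a natural sequence: weak enhancement leads to an adjustment, and absent enhancement after six patients leads to closure. The triggers do differ, and the protocol calls the closing event unlikely. This narrows the conflict to the case of no enhancement with six patients evaluated. It does not remove it, because no order is written and (C) has no patient count. A reader might infer that the rules collide at any time up to six patients. They do not, because neither terminating rule can act before six.

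A reader might also see a contradiction between (B) or (C) and the statement in (D), "This is the reason why we limit our study population to this dose for this initial pilot study". The text around it points to a later grant for subgroups at decreasing doses, so it reads naturally as saying that this pilot has no planned dose-ranging. Nor do the case report forms prevent recovery of the dose given. They pre-print 5 mg/kg but also record weight and actual injection volume.

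On the plateau, an unreachable number by itself triggers nothing, and the terminating sentences use the word without a number. That stands, and it makes this part a request for clarification. It would go too far to say that the criterion is impossible on every scale.

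On the analysis, it can fairly be said that this is a pilot whose key estimates are the SD and CV, and that Section 11.2.2 does not specify one single AUC and test. The large figures above arise mainly at CV 15% or in the extreme split. The balanced-split loss also depends on the noise scaling with dose: if only the means scale, power is 73%, 82% and 84% (sarcoma basis) against 76% with no change. All of this stands. The silence on dose remains.

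**Conclusion.** The point holds and is minor. Three things rest on the text alone:

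- With six patients evaluated and no enhancement seen, Section 6 prescribes both a dose change and termination, in no stated order.
- The only numeric plateau criterion cannot be met for T2 as an ordinary percent signal loss, and Section 6 does not say which measure it means.
- Section 11.2 would mix dose levels that the protocol permits.

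Confounding of dose with diagnosis follows only if a dose is changed and the change falls unevenly. The documents do not predict that. Its size is unknown: the simulated figures show that it could matter at a low CV with a lopsided split, and that it matters little for a balanced change at CV 30–50% or for a large true contrast. They should not be read as a forecast of bias.

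**What to change.** The investigators should reconcile dose modification (C), dose modification (D) and study stopping rule (C). The text should say which acts first, on how many patients and which sequences each is judged, and on what scale the plateau is measured. No dose or clinical rule is proposed here.

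In Section 11 add wording to this effect: if more than one dose level is used, the dose given will be tabulated by diagnosis; a dose-stratified or single-dose-level AUC and rank sum result will be shown beside the pooled result; and the pooled result will not be interpreted alone when dose is unbalanced between diagnoses. A van Elteren test is one option for the stratified result. The dose given in mg Fe/kg is actual injection volume (ml) × 30 mg Fe/ml ÷ weight (kg), all already on the forms or in Section 4.

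The cost is amendment wording and a short addition to Section 11, with no new data. The addition has no effect if one dose is used throughout. The drawback is power. In the uneven example only 4 sarcomas and 10 osteomyelitis patients share a dose, and power at 1.33 SD is about 45% (exact rank sum) to 52% (van Elteren, normal approximation). If dose and diagnosis are completely confounded, no analysis can separate them.
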